Boiled Oral Peanut Immunotherapy for the treatment of Peanut Allergy (The BOPI Study)

Version 2.6 dated 5 June 2018

SPONSOR: Imperial College London

FUNDING: Imperial/NIHR Biomedical Research Centre

STUDY CENTRE: Imperial College London

NRES reference: 15/LO/0287

Protocol authorised by:

Name & Role Date Signature

Version 2.6, 5 June 2018

PROTOCOL SYNOPSIS

Title	Boiled Oral Peanut Immunotherapy for the treatment of Peanut Allergy		
Abbreviated title	BOPI study		
Clinical Trials.gov number	NCT02149719		
NREC Number	London Central 15/LO/0287		
Sponsor R&D Number	15SM2492		
IRAS Number	158693		
Primary objectives	To evaluate the effectiveness of Oral Immunotherapy (OIT) using boiled peanut to induce desensitization to roasted peanut in children with IgE-mediated peanut allergy		
Intervention	Randomised open trial of 12 months of oral immunotherapy using a combination of boiled followed by roasted peanut. Control group receive standard clinical care, with option to undergo OIT after 12 months.		
	Clinical reactivity to roasted peanut will be determined pre- and post-OIT using double-blind, placebo-controlled food challenge.		
	Participants will be invited to return after 3 years for a set of assessments to determine longer-lasting tolerance to peanut.		
Safety	Food challenges and updosing will take place in a dedicated hospital paediatric research unit, by personnel qualified in the recognition and treatment of anaphylaxis, and observed for at least 60 minutes following a dose.		
	All families will be provided with an Allergy Management Plan, rescue medication including adrenaline autoinjector devices, and appropriate training in the recognition and management of allergic reactions.		
Patient group	Children and young people with a diagnosis of IgE-mediated peanut allergy between 8 -16 years old. Target recruitment of 46 subjects		
Sponsor	Imperial College London		
Funding	NIHR Biomedical Research Centre at the Imperial Academic Health Sciences Centre (AHSC), a partnership between Imperial College Healthcare NHS Trust and Imperial College London.		

Study Management

Chief Investigator: [name], Imperial College London

Co-investigators: [name], Imperial College London

[name], Imperial College London [name], University College Cork [name], University of Sydney, Australia [name], Children's Hospital at Sydney, Australia [name], Medway School of Pharmacy,

Study Management: [name], Imperial College London

Independent Data Monitoring Committee

				3) Changing some of the in-hospital updosing stages into a split-dose procedure where there had been a change in boiling time e.g. rather than give 4 peanuts as a single dose, to split this into 1 peanut followed by 3 peanuts 30 minutes later [section 5.3.4.1]
2	2.2	9 Dec 2015 approved 15.12.15	[name]	 Assess a mobile 'app' as an alternative to the patient diaries currently being used [sections 5.3.3 and 5.3.4] Extended laboratory work [section 5.7.3] Recruit via PIC sites [section 5.1]
3	2.3	28 Jan 2016 Approved 16 Feb 2016	[name]	 Extension of observation times following challenges to minimum 2 hours [sections 5.3/5.4] Clarification of SPT at 6 month visit revised (non- substantial amendment) [section 5.7.1]
4	2.4	8 April 2016 Approved 24 Apr 2016	[name]	 Inclusion of cardiac echocardiography as a non-invasive assessment [section 5.2.3] Extend laboratory work on patient samples section 5.7.3]
5	2.5	8 Feb 2017 Approved 19 Apr 2017	[name]	 Inclusion of DNA collection (opt-in) [section 5.2.3] Increase in blood sample volume to max 75ml per visit (no change in per kg body weight volume) Clarifications: Blood analyses at challenge (5.2.3) Addition of blood sample at 13 months (5.7.3) Correction of typo in 12mth challenge (5.4.1) Updated co-investigators 24hr follow-up after challenges (5.2.2) Use of peanut M&Ms instead of peanut (5.3.4.4)
6 (minor)	2.5	22 Mar 2018 Approved 19 Apr 2018	[name]	Extension to study end date (minor, no changes to protocol)
7	2.6	5 June 2018 Approved 21 Jun 2018	[name]	 Addition of year 3 assessments with associated extension to study end date (section 5.7). Change in maintenance dose beyond 1st year to thrice weekly dosing (section 5.4.2)

Version 2.6, 5 June 2018

GLOSSARY OF ABBREVIATIONS

ABBREVIATION	TERM
AE	Adverse Event
BSACI	British Society for Allergy & Clinical Immunology
DBPCFC	Double blind, placebo-controlled food challenge
FAQL-Q	Food Allergy Quality of Life - Questionnaire
IDMC	Independent Data Monitoring Committee
LOAEL	Lowest observed adverse event level
NOAEL	No observed adverse event level
OIT	Oral Immunotherapy
PN	Peanut
PSS	Perceived Stress Scale
QoL	Quality of Life
SAE	Serious adverse event
SAR	Serious adverse reaction
SCORAD	SCORing Atopic Dermatitis tool
SPT	Skin Prick test

Version 2.6, 5 June 2018

TABLE OF CONTENTS		
PROTOCOL SYNOPSIS		2
AMENDMENT HISTORY		4
GLOSSARY OF ABBREVIATIONS		5
1. INTRODUCTION		8
1.1 BACKGROUND		8
1.2 STUDY RATIONALE & JUSTIFICATION		8

1. INTRODUCTION

1.1 BACKGROUND

Peanut allergy is the most common cause of severe allergic reactions to food.¹ Onset is common in childhood, but in contrast to other food allergies such as cow's milk and egg, peanut allergy tends to persist into adulthood.² It is associated with a significant impact on quality of life, both for the affected individual and their family.

There is no current cure for peanut allergy. Oral peanut immunotherapy (OIT) using roasted allergen has been demonstrated to offer potential in this regard, but is associated with significant and frequent reactions and can cause life-threatening allergic symptoms.³ Furthermore, although study regimes have been relatively successful in inducing transient desensitisation, most have not assessed for the induction of sustained unresponsiveness; where this has been investigated, OIT (typically under 6 months duration) has been largely unsuccessful in demonstrating when daily allergen is ceased.⁴ A recent study involving peanut OIT for 12-18 months appears to be more successful in inducing sustained unresponsiveness,⁵ which is consistent with the clinical data for immunotherapy to aeroallergens. Current protocols generally mandate increases in dose during induction to take place under medical supervision, due to the frequency and unpredictable nature of reactions experienced. This places a significant burden on families of children undergoing OIT, due to the need for frequent hospital visits along with observation after dosing at home.

We have previously demonstrated that the processing of peanuts through boiling results in a relatively hypoallergenic product due to the loss of key allergenic components from peanut into the water.⁶ Our pilot has demonstrated that a desensitization protocol, using boiled peanut, can successfully result in desensitization to raw peanut; ongoing follow-up suggests these children also demonstrate desensitization to roasted peanut, but this has not been formally studied. The use of boiled peanut was well-tolerated with minimal symptoms at updosing, suggesting that this approach may well be appropriate as a safer, better tolerated approach to achieving successful OIT, with the possibility of improved sustained tolerance.

1.2 STUDY RATIONALE & JUSTIFICATION

We wish to formally assess, in a randomized controlled study, whether a modified approach using boiled peanut for peanut OIT can result in desensitisation and sustained unresponsiveness (i.e. tolerance) to roasted peanut. We will assess the safety of this approach, and study the immunological mechanisms involved, our secondary aim being to develop clinically-useful predictors for identifying individuals likely to undergo successful desensitization.

STUDY HYPOTHESIS:

A pragmatic protocol utilizing increasing doses of boiled peanut can induce desensitisation to roasted peanut, in peanut-allergic individuals, with an acceptable safety profile.

¹Turner PJ, Gowland MH, Sharma V, et al. Increase in anaphylaxis-related hospitalizations but no increase in fatalities: An analysis of United Kingdom national anaphylaxis data, 1992-2012. JACI 2014; doi: 10.1016/j.jaci.2014.10.021.

²Bégin P, Paradis L, Paradis J, Picard M, Des Roches A. Natural resolution of peanut allergy: a 12-year longitudinal follow-up study. JACI In Practice 2013;1:528-30.e1-4.

³Wood RA, Sampson HA. Oral immunotherapy for the treatment of peanut allergy: is it ready for prime time? IACI In Practice 2014;2:97-8.

⁴Vickery BP, Scurlock AM, Kulis M, et al. Sustained unresponsiveness to peanut in subjects who have completed peanut oral immunotherapy. JACI 2014;133:468-75.

⁵Tang ML, Ponsonby AL, Orsini F, et al. Administration of a probiotic with peanut oral immunotherapy: A randomized trial. J Allergy Clin Immunol. 2015. doi: 10.1016/j.jaci.2014.11.034.

⁶Turner PJ, Mehr S, Sayers R, et al. Loss of allergenic proteins during boiling explains tolerance to boiled peanut in peanut allergy. JACI 2014;134:751-3.

2. STUDY OBJECTIVES

2.1 PRIMARY OBJECTIVE

• To evaluate the effectiveness of OIT using boiled peanut to induce desensitization to roasted peanut in children with IgE-mediated peanut allergy.

2.2 SECONDARY OBJECTIVES

- To evaluate the safety of peanut OIT in children with IgE-mediated peanut allergy.
- To assess the rate of sustained unresponsiveness following peanut OIT
- To identify predictors which can identify individuals likely to undergo successful desensitization and sustained unresponsiveness using boiled peanut
- To assess the impact of peanut OIT on quality of life (QoL) measures, both from the child/young person's perspective as well as their parents'.
- To assess how duration of OIT impacts on sustained unresponsiveness

3. STUDY DESIGN

London

The study consists of 2 related work packages (see Figure 1):

WP1: A 52 week, phase 2 single centre open label interventional randomized controlled trial to assess the efficacy of OIT using boiled peanut to induce desensitization in children with IgE-mediated peanut allergy. Participants will be randomized 2:1 to active intervention or control (current best standard care, i.e. strict peanut avoidance plus provision of rescue medication and training) for 12 months.

WP2: Subjects in the active group will undergo a 4 week period OFF peanut intake, followed by an unblinded peanut challenge to assess for sustained unresponsiveness. Those who pass the challenge will continue weekly maintenance with roasted peanut, those who fail will resume daily peanut for a further year.

Subjects in the control group will be offered the option of receiving the active intervention following the 12 month control phase (boiled peanut immunotherapy). This will allow confirmation that the two groups are similar in response to OIT using boiled peanut, increasing the precision of the results.

[figure not shown]

Figure 1: CONSORT diagram for the BOPI study. [PN: Peanut; SU: Sustained unresponsiveness]

Summary of Study components:

- 1. **Recruitment and eligibility screen**: Peanut-allergic subjects will be recruited from both our local patient population and through our local paediatric allergy network in North West London.
- 2. **Initial double-blind, placebo-controlled food challenge** (DBPCFC) to roasted peanut. This will demonstrate true clinical reactivity to roasted peanut rather than sensitization alone, as it is unethical to undertake peanut OIT in children who are not clinically allergic to roasted peanut.
- 3. **Randomisation and WP1:** Peanut-allergic children will be randomized 2:1 to either active treatment (OIT using boiled PN) or control (current best practice, i.e. strict peanut avoidance plus provision of rescue medication and training) during months 0-12.
- 4. **1 year assessment:** At 12 months, all subjects will undergo a DBPCFC to roasted PN, to assess for ongoing clinical allergy (and determine threshold of reactivity) to roasted PN. Subjects in the active group will stop all peanut for 4 weeks and then undergo a further open challenge to assess for sustained unresponsiveness (ie. tolerance without the need for ongoing peanut exposure).
- 5. **WP2:** Those subjects in the control group will be offered OIT using boiled PN during months 12-24. Subjects in the active intervention groups will be offered ongoing maintenance therapy within the study protocol.
- 6. **2 year assessment** and option to determine longer-term tolerance to peanut.

Subjects will be invited to remain in the study for a 3rd year to allow longer-term evaluations to be performed.

The efficacy and impact of OIT on quality of life will be assessed at 6, 12, 24 and 36 months in all subjects (and their parents), using a validated questionnaire.

3.1 STUDY OUTCOMES MEASURES

3.1.1 PRIMARY STUDY OUTCOME

• The proportion of participants who tolerate 1.4g (or more) roasted peanut protein (equivalent to ≥ 6 roasted peanuts) after 12 months of OIT as assessed by DBPCFC, in the active vs control group.

3.1.2. SECONDARY STUDY OUTCOMES

- Relative change in clinical threshold (No observed adverse event level, NOAEL; Lowest observed adverse event level, LOAEL) to roasted peanut at 6 and 12 months.
- Rate of sustained unresponsiveness after 4 week cessation of maintenance OIT at 1 year and 3 years.
- Change in quality of life (QoL) assessments at 6 and 12 months after OIT, as assessed by FAQL-Questionnaire in children, teenagers and their parents in the active vs control group.
- Safety of OIT using boiled peanut as defined by frequency and nature of allergic symptoms experienced.
- Compliance with study protocol
- Immunological outcome measures pre-, during and post-OIT

3.2 STUDY DESIGN RATIONALE

The is a **randomized controlled** study, utilizing a control group with a delayed start to control for the incidence of natural resolution of peanut allergy over 12 months. Natural resolution of peanut allergy occurs in 10%-20% of peanut allergic children over a longer time period. Inclusion of a control group also facilitates the assessment of the safety of OIT and QoL measures (by comparing active to control patients who may experience accidental allergic reactions despite best management).⁷

Controls will be offered a deferred start to OIT (using boiled peanut) after 12 months on current standard care (avoidance advice and provision of a rescue plan and medications in the event of an accidental allergic reaction). We consider it unethical not to offer control participants the opportunity to undergo active treatment having undertaken peanut challenges during the 12 months of non-intervention. We also expect that this design will encourage compliance with the study protocol.

To avoid selection bias, participants will be randomized to active or control groups. A level of stratification will be included to distinguish between those who are predominantly sensitized to a specific peanut protein epitope (Ara h 2). This is because pilot data indicates that the boiling process affects leaching of Ara h 2 from peanut more than other proteins. Patients who are predominantly sensitized to Ara h 2 may be more likely to have a successful outcome than those allergic to other peanut proteins. The stratification will reduce the risk of skewing the results through randomization.

As with most OIT studies, this study will be **open label**, as we wish to assess a pragmatic approach to dosing which would not be possible with blinding. Families will be provided with a specific peanut cultivar (Holt Runner, Peanut Company of Australia Ltd); families will be given specific instructions on preparing the peanut for OIT (through boiling) at home. The supply of raw peanuts direct from the wholesaler also reduces potential nut-contamination. We have chosen a specific cultivar with higher oleic oil content, resulting in a longer shelf-life (at least 18 months when vacuum packed and stored at 4°C). To perform OIT safely, supervision and frequent appointments to the research unit are required. A blinded study would increase the burden on families. Finally, the use of blinding might lead participants (and their families) to believe they are indeed tolerant to peanut and therefore result in less stringent allergen avoidance, putting them at increased risk of accidental reactions.

We have chosen a daily maintenance dose of 800mg roasted peanut protein, on the basis of previous reports that this amount is generally well-tolerated by subjects undergoing OIT on an daily basis, and is also associated with a suggestion of efficacy. Our primary endpoint (able to tolerate 1.4mg roasted peanut protein, equivalent to \geq 6 roasted peanuts) has been chosen on the basis of efficacy and ability to protect against accidental exposure to peanut in the community. This will be assessed using a blinded food challenge, an established research tool in food allergy.

The inclusion of an assessment to determine tolerance (sustained unresponsiveness) to peanut in the absence of ongoing daily peanut exposure is essential. The realities of day-to-day life mean that outside the safety of a clinical trial, maintenance peanut doses are often omitted. It is therefore important to demonstrate ongoing tolerance to peanut in the absence of daily maintenance. Furthermore, the reassurance through the demonstrated tolerance in children with previous peanut allergy may well improve quality of life further. This outcome needs to be corrected for the possibility of natural resolution, thus a comparison to controls who have not undergone OIT is required.

The study has been designed as a **single centre** study: the procedures involved are complex and require intensive clinical assessment only available at a specialist allergy centre. The use of a single centre allows a more efficient use of resources and promotes consistency in clinical management. Our location (in central London) allows for the recruitment of patients from a diverse geographical area and ethnic background.

⁷Anagnostou K, Islam S, King Y, et al. Assessing the efficacy of oral immunotherapy for the desensitisation of peanut allergy in children (STOP II): a phase 2 randomised controlled trial. Lancet. 2014;383(9925):1297-304.

⁸Plaut M, Sawyer RT, Fenton MJ. Summary of the 2008 National Institute of Allergy and Infectious Diseases–US Food and Drug Administration Workshop on Food Allergy Clinical Trial Design. J Allergy Clin Immunol 2009;124:671-8.e1.

4. STUDY POPULATION

4.1. INCLUSION CRITERIA

- 1. Age 8-16 years.
- 2. Past history of peanut allergy, with:
 - Previous clinical reaction with ongoing sensitisation to peanut, OR positive allergy test to peanut (either skin prick test ≥8mm or serum specific IgE > 15kUA/I) to peanut consistent with >95% likelihood of clinical allergy⁹, AND
 - further confirmation of clinical reactivity to roasted peanut at double-blind placebo-controlled food challenge at screening
- 3. Tolerates at least ¼ boiled peanut (boiled for 4 hours) at open food challenge at screening.
- 4. Full informed consent of parent/legal guardian and patient assent.

4.2. EXCLUSION CRITERIA

- 1. Required previous admission to an intensive care unit for management of an allergic reaction to peanut.
- 2. Clinically significant chronic illness (other than asthma, rhinitis or eczema).
- 3. Undergoing subcutaneous or sublingual immunotherapy and within the first year of therapy, for respiratory allergy.
- 4. Subjects receiving anti-IgE therapy, oral immunosupressants, beta-blocker or ACE inhibitor.
- 5. Clinical allergy to either soya or sunflower seed
- 6. Tolerance to ≥1.4 g peanut protein (approx. 6 peanuts) at initial DBPCFC during screening.
- 7. Subjects allergic to ¼ boiled peanut (boiled for 4 hours) at screening.
- 8. Poorly controlled asthma within the previous 3 months (as defined by clinician judgement with reference to the ICON consensus¹⁰), or asthma requiring oral corticosteroid therapy within the previous 3 months.
- 9. Pregnancy
- 10. Unwilling or unable to fulfil study requirements

4.3. WITHDRAWAL CRITERIA

Subjects will be free to withdraw from the study at any time without affecting their future medical care. Subjects who are withdrawn from active treatment will remain in the study for assessment of outcome relating to QoL measures.

The safety of the child is paramount in this study. Thus, children who experience anaphylaxis to an OIT dose at home, but who do not receive IM adrenaline as per the management plan, will have further updosing suspended until the family undergo retraining on the recognition and management of allergic symptoms.

A participant will be withdrawn from the study under the following circumstances:

- If, in the opinion of the study team, compliance with study procedures is suboptimal such that it compromises the patient's safety.
- If, in the opinion of the study team, further participation would adversely affect the participant's health.
- A child develops an exclusion criteria during the updosing phase of the study e.g. a new medication (which would normally be a contra-indication) is commenced.
- If consent is withdrawn or the subject fails to return for a study visit.
 In the event of a serious adverse reaction to OIT and/or if presenting with anaphylaxis requiring more than one IM adrenaline dose within 2 hours after an OIT dose.

Any subject excluded from further participation will not be replaced.

⁹ Sporik R, Hill DJ, Hosking CS. Specificity of allergen skin testing in predicting positive open food challenges to milk, egg and peanut in children. Clin Exp Allergy 2000; 30:1540–6.; AND Sampson HA. Utility of food-specific IgE concentrations in predicting symptomatic food allergy. J Allergy Clin Immunol 2001;107: 891–6.

¹⁰Papadopoulos NG, Arakawa H, Carlsen KH, et al. International consensus on (ICON) pediatric asthma. Allergy. 2012;67:976-97.

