5 STUDY PROCEDURES

The main study procedures are shown in Figure 2, and consist of the following stages:

- 1. Recruitment and initial screening
- 2. Initial double-blind, placebo-controlled food challenge (DBPCFC) to roasted peanut.
- 3. **Randomisation and WP1:** Following demonstration of tolerance to one boiled peanut, peanut-allergic children will be randomized 2:1 to either active treatment (OIT using boiled PN) or control (current best practice) during months 0-12.
- 4. **1 year assessment:** All subjects will undergo a DBPCFC to roasted PN, to assess for ongoing clinical reactivity (and determine threshold of reactivity) to roasted PN. Subjects in the active group (Group A) will stop all peanut for 4 weeks and then undergo a further open challenge to assess for tolerance (i.e. sustained unresponsiveness without the ongoing peanut exposure).
- 5. **WP2:** Children in the control group (Group B) will be offered OIT using boiled PN during months 12-24. Subjects in the active intervention groups will be offered ongoing maintenance therapy within the study protocol.
- 6. 2 year assessment and option to determine longer-term tolerance to peanut.

[figure not shown]

Figure 2: Study flowchart and interventions

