5.2.1 CLINICAL ASSESSMENT AND CHECKS PRIOR TO DBPCFC

All subjects will be assessed prior DBPCFC to determine suitability for a challenge, as follows:

- No intercurrent illness (viral or otherwise)
- No exacerbation in allergic symptoms (eczema, asthma, food allergy) in the preceding week.
- No short-acting β2 agonists used in the past 12 hours
- No short-acting antihistamine taken (e.g. cetirizine, loratadine) in the past 48 hours (72 hours for fexofenadine)
- No long-acting antihistamine (e.g. chlorphenamine, desloratadine) in the previous 5 days.
- No oral steroids have been taken in the past 2 weeks

¹¹Kunz, B., Oranje, A.P., Labreze, L., Stalder, J.F., Ring, J., and Taieb, A. Clinical validation and guidelines for the SCORAD index: consensus report of the European Task Force on Atopic Dermatitis. Dermatology. 1997; 195: 10–19

¹²Sampson HA, Gerth van Wijk R, Bindslev-Jensen C, et al. Standardizing double-blind, placebo-controlled oral food challenges: AAAAI-EAACI PRACTALL consensus report. J Allergy Clin Immunol. 2012;130:1260-74.

- Baseline observations (temperature, blood pressure, heart and respiratory rate, oxygen saturation) within normal range.
- Baseline physical examination must not reveal any significant acute findings.

Challenges will occur on a Paediatric Allergy Research Unit (PRU) where food challenges are performed on a regular basis, and staff are familiar with the management of allergic reactions including anaphylaxis through clinical experience and regular training. Emergency equipment (including oxygen and suction) and medication will be checked beforehand, as per local protocol and international criteria for performance of DBPCFC.

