5.3.4.1 UPDOSING

At each step (i.e. all dose increases), the dose will first be given under medical supervision on the Research Unit, followed by observation for at least one hour (2 hours if participant has previously experienced a delayed reaction). Prior to a dose increase, the supervising clinician will assess the participant to ensure:

- No significant allergic reactions to doses given in previous 2 weeks.
- No acute exacerbation of asthma in the past week.
- No concurrent systemic illness.

The dose can be mixed into a carrier (such as low fat (rather than full fat) yoghurt, for example) if desired. Children will be monitored under medical supervision for one hour following dose administration. Following each dose increase, that dose will be given to participants at home daily for a minimum of 2 weeks until the next increase is performed.

STEP	PEANUT Boiling time	No. of peanuts / day	No. weeks at this dose (minimum)	Cumulative No. of weeks (minimum)	Approximate Peanut protein (mg)
pre-A	4 hours	1/8	2	-	15
pre-B	4 hours	1/4	2	-	30
1	4 hours	1/2	2	2	65
2	4 hours	1	2	4	130
3	4 hours	2	2	6	260
4	4 hours	4	2	8	520
5	4 hours	8	2	10	1040
6	2 hours	4*	2	12	520
7	2 hours	8	2	14	1040
8	1 hour	2*	2	16	260
9	1 hour	4	2	18	520
10	1 hour	8	2	20	1040
11	1/2 hour	4*	2	22	520
12	1/2 hour	8	4	26	1040
	Open OFC to	roasted peanut (t	o determine if u	pdosing can be co	onverted to roasted):
		_	=	•	anuts up to Wk 52
	• If tole	erates 300mg dose	e, continue updo	osing as follows:	
13	n/a	½ roasted PN	4	30	125
14	n/a	1 roasted PN	4	34	250
15	n/a	2 roasted PN	4	38	500
16	n/a	4 roasted PN	4	42	1000

Table 1: Updosing protocol for Peanut (PN) OIT using boiled and then roasted peanut.

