5.3.4.4 PREPARATION OF BOILED AND ROASTED PEANUT FOR OIT

Families will be provided with blanched raw peanut at hospital visits, for preparation at home. Full instructions will be provided (as part of the **home diary and instruction sheet**). Peanuts (Holt Runner cultivar, supplied by the Peanut Company of Australia Ltd) will be supplied in 125g vacuum-packed batches to families on an as-needed basis, in order to monitor peanut consumption.

Families will be provided with instructions to boil the peanuts at home in batches, as follows:

- Boil 100g quantity of peanuts in a saucepan in ~600ml water for xx hours
- Drain and plunge peanuts into cold water, then drain in colander/sieve
- Lay peanuts in a single layer on a baking tray lined with baking paper
- Place tray in freezer until peanuts are 'snap frozen'
- Transfer peanuts into a plastic container and store in freezer until required.

The boiling time will be progressively reduced as depicted in Table 1 above.

In those children who tolerate roasted peanuts, families will be instructed to use commercial roasted peanuts (KP roasted peanuts) sourced from a UK supermarket. Alternatively, peanut M&Ms may be substituted for roasted peanut, where this is desired by the study participant: four roasted peanuts is equivalent to 6 peanut M&Ms.

5.4 1 YEAR ASSESSMENT

All subjects, in both the active (OIT) and control groups, will be invited to undergo a further DBPCFC to roasted PN at 12 months. Those who tolerate >1.4g of peanut protein at this challenge will be invited back for a further open challenge having stopped all peanut ingestion (including OIT doses) for 4 weeks. The challenges and outcomes are depicted in summary form in Figure 7.

[figure not shown]

Figure 7: Challenges and outcomes, months 12-13

All subjects will also undergo repeat skin prick testing to commercial crude peanut extract, and quality-of-life assessments as described in section 5.7.1.

Imperial College

5.4.1 12 MONTH DBPCFC

The DBPCFC will be performed as per Protocol 1 in Section 5.2.2. The purpose of this challenge is:

- In those who have undergone OIT, to assess for desensitisation to roasted peanut and a resulting change in threshold of clinical reactivity (Primary and Secondary outcome measures).
- In the control group, to determine the rate of natural resolution of peanut allergy and for those continuing into WP2 (where they will undergo OIT), serve as the baseline threshold of clinical reactivity to roasted peanut.

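### Read literally, section 4.3 can cost an OIT child, but not a control with the same temporary event, the 12-month DBPCFC

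*Combined protocol and SAP*

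**What the plan says.** Section 4.3 gives a list of circumstances in which a participant is taken out of the study. One entry is "A child develops an exclusion criteria during the updosing phase of the study", with a newly started contraindicated medicine as its example. The entry does not require the exclusion to be lasting, and it gives no route back.

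On follow-up after treatment stops, 4.3 says: "Subjects who are withdrawn from active treatment will remain in the study for assessment of outcome relating to QoL measures". Section 7.2 repeats the sentence. Neither mentions the DBPCFC.

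Other sections lean the other way:

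- Section 5, on the 1-year assessment: "All subjects will undergo a DBPCFC to roasted PN, to assess for ongoing clinical reactivity".
- Section 5.4: "All subjects, in both the active (OIT) and control groups, will be invited to undergo a further DBPCFC".
- Section 7.2 specifies an intention-to-treat primary analysis, whatever the compliance or completion of the regimen.
- Section 8.2 keeps children in follow-up and analysis when a clinician departs from the protocol treatment.

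The primary outcome (3.1.1) is tolerance of at least 1.4 g roasted peanut protein at the 12-month DBPCFC, so without that challenge there is no primary outcome.

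**The concern.** Before month 12 the updosing phase exists in one arm only. Section 5.3.4.1 describes it for the OIT arm. Controls avoid peanut for 52 weeks (5.3.3) and are offered OIT in months 12-24 (5.5), after their own 12-month challenge. This bullet therefore cannot reach a control before the primary endpoint.

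The trigger need not be caused by OIT. A short course of a contraindicated medicine can happen in either arm. Whether the primary outcome is then measured could depend on allocation, which works against the intention-to-treat analysis in 7.2. If the children lost in this way differ in outcome from the rest of their arm, leaving them out biases the comparison. If they do not differ, leaving them out does not bias the OIT rate.

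**Working it through.** **1. The same event in each arm.** Take a temporary exclusion that arises while an OIT child is updosing and resolves well before month 12.

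- *Contraindicated medicine, short course.* OIT child: 4.3 applies by its own example, and the child leaves the study. Control: not updosing, so the bullet does not apply and the invitation in 5.4 stands.
- *Oral steroid course for asthma at month 5.* Exclusion criterion 8 covers "asthma requiring oral corticosteroid therapy within the previous 3 months". An OIT child still updosing meets it and, on a literal reading, leaves the study. A control with the same course stays. At month 12 the relevant check in 5.2.1 is "No oral steroids have been taken in the past 2 weeks", which a month-5 course passes. This example is arguable (see the objection).
- *Lasting exclusion (pregnancy, long-term beta-blocker).* Not clearly one-sided. A control's challenge could also be prevented by the 4.3 entry on cases where "further participation would adversely affect" the child's health, or by the 5.2.1 checks.

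**2. How long the bullet can act.** From Table 1, the shortest scheduled updosing runs from a start at Step 5 to the end of Step 12: 26 − 8 = 18 weeks. The longest runs from pre-A to the end of Step 16: 4 + 42 = 46 weeks. These are minimum durations, because the steps are minimum times.

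**3. The plan's sample size.** Inputs from 7.1: 60% v 10%, two-sided 0.05, 80% power, continuity correction, 2:1 allocation, 20% loss, N = 46 (30 v 16).

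- Pooled proportion: (0.10 + 2 × 0.60)/3 = 0.433.
- Controls without correction: n = [1.96·√(0.433 × 0.567 × 1.5) + 0.842·√(0.10 × 0.90 + 0.60 × 0.40/2)]² / 0.5² = 9.92.
- With correction: (n/4)·[1 + √(1 + 2 × 1.5/(n × 0.5))]² = 12.75 controls, so 3 × 12.75 = 38.25 in total.
- Allowing for loss: 38.25 × 1.2 = 45.9, or 38.25/0.8 = 47.8.

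The stated 46 is reproduced to within 2 children, and the point does not rest on it.

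**4. Possible bias.** The documents give no rate for this event. I assume k = 1, 2 or 3 of 30 OIT children lose the challenge and no control does, with 18 of 30 true OIT successes expected.

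| k lost | Left out, all true failures: 18/(30−k) | Left out, all true successes: (18−k)/(30−k) | Counted as failures, loss unrelated to outcome: 0.6(30−k)/30 |
|---|---|---|---|
| 1 | 62.1% | 58.6% | 58% |
| 2 | 64.3% | 57.1% | 56% |
| 3 | 66.7% | 55.6% | 54% |

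The first two columns are the extremes when children are left out. Loss unrelated to outcome leaves 60% unchanged.

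**5. Power.** Exact power of the two-sided Fisher test (p < 0.05) at true rates 60% v 10%:

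- 30 v 16, none lost: 93.4%.
- k = 1, 2, 3 counted as failures, with OIT successes distributed as Bin(30−k, 0.6): 91.6%, 89.4%, 86.9%.
- The whole 20% allowance used (6 OIT, 3 control): 85.3% if left out (24 v 13), 82.9% if counted as failures in 30 v 16.

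All exceed the planned 80%.

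**The case against.** The best case against the point is that the protocol, read as a whole, keeps these children. Sections 5 and 5.4 plan the challenge for all subjects, 7.2 specifies intention to treat, and 8.2 arguably covers 4.3's own example of a new medicine. The protocol also uses withdrawal loosely. The 12-month outcome table in 5.4.1 applies it to children whose OIT failed, yet 5.7 invites every child back at year 3. Children withdrawn after a significant reaction are also contacted again (5.8.2, Appendix 3).

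This makes retention a plausible reading, so the defect is a conflict between sections rather than a settled decision to drop the endpoint. It does not remove the conflict. The statements about all subjects do not say that they include a child already withdrawn. Intention to treat does not supply a challenge that was never done. The further contact in 5.8.2 and Appendix 3 is QoL and interview only.

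The steroid example is also open to challenge. Section 5.3.4.1 requires before a dose increase: "No acute exacerbation of asthma in the past week". That check has no severity limit, and failing it delays the dose. A team could reasonably treat a steroid-treated exacerbation as a pause, and criterion 8 is written for entry. That stands: the example is arguable, and the short course of a contraindicated medicine is the cleaner case.

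A reader might infer that every asthma flare, or every new exclusion, removes OIT children only. The documents do not support this, given 5.3.4.1 for asthma and the health and pre-challenge rules that reach controls with lasting exclusions.

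**Conclusion.** The point holds as a conflict in wording with a possible one-sided effect. Followed literally, one bullet in 4.3 can remove the primary outcome for an OIT child where a control with the same temporary event would keep it, and no other section says that it takes precedence.

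The size is unknown and probably small. With 1 to 3 of 30 children left out, the OIT rate moves by at most about 7 points (60% to 66.7%), and only if all three were true failures. The range rests on my assumed counts, on the 60% rate in 7.1 and on no control being lost.

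Two stronger readings are tempting. One is that the rule favours OIT. The documents do not show this: the direction depends on who is lost and how they are counted, and counting them as failures works against OIT. The other is that the trial loses its power. It does not: these losses fall within the planned 20%, and power stays above 80% even with that whole allowance used.

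This is a low-cost improvement to consider, held with medium confidence.

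**What to change.** 1. Delete this bullet from the study-withdrawal list in 4.3. Left there, any wording that keeps the child in the study would contradict the list's heading. Put a separate paragraph in 4.3:

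> If a child develops an exclusion criterion during updosing, OIT dosing is paused or stopped at the clinician's decision. The child remains in the study and is offered the 12-month DBPCFC on the same terms as controls, if the 5.2.1 checks are met and the challenge is judged safe.

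2. In both 4.3 and 7.2, amend the sentence on subjects withdrawn from active treatment so that they stay in the study for QoL measures and, where safe, the 12-month DBPCFC.

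The cost is one moved paragraph and two amended sentences. No procedure is added, because the challenge is already planned for all subjects. The downside is that a few children off OIT undergo a supervised challenge with its risk of reaction, as controls already do. Stopping or pausing OIT remains a clinical decision.

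Two gaps stay open. Section 7.2 still has no rule for a 12-month DBPCFC that is missing; the edit only makes that rarer. The serious-adverse-reaction ground in 4.3, which is tied to OIT doses, also stays in the study-withdrawal list and needs its own decision.
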